8.7 FOLLOW UP VISITS

Follow-up visits will be conducted at 1 month, 6 months, and annually for 3 years post implant procedure intervals as illustrated in Table 11. The following procedures will be conducted during follow up visits:

1. Clinical Evaluation Hospitalizations and/or Clinic Visits and Paracentesis, Concomitant Medications and doses, Edema Grading, ankle circumference measurements, and NYHA classification
2. Administration of Health Status Questionnaires (e.g., SF-12, KCCQ)
3. Administration of Six Minute Walk Test
4. Administration of Patient Edema Questionnaire
5. Safety Evaluation
6. Clinical Laboratory Tests :
 - a. CBC and platelet count
 - b. Complete metabolic panel
 - c. Liver panel
 - d. INR and PTT/aPTT
 - e. Serum creatinine and eGFR
7. Standard 12-lead ECG
8. Comprehensive Transthoracic Echocardiogram (TTE) per echo core lab acquisition protocol
9. Modified Rankin Scale (mRS): mRS will be conducted for all patients who had a stroke since their last assessment. It is recognized that an assessment of stroke is incomplete without an appropriate measurement of the disability resulting from the stroke, hence, mRS closest to 90 days post event will be used to assess clinical disability. Every effort should be made to have a neurologist or neurology fellow perform the neurological assessments, or alternatively, a by a trained research team member certified in stroke assessment. mRS can be obtained by a certified research team member via phone interview with the patient or caregiver member if the patient is unable to visit the research office.

Follow-up data to be collected will include but is not limited to the information listed in the following table:

Table 10 – Follow-Up Visit Information

| General Information | Clinical Information | Laboratory Measurements |
|--|--|---|
| 
 • Visit date • Height • Weight | 
 • Clinical evaluation (mobility, edema grading, ankle circumference measurements, ascites, access site) • Vital signs (Blood Pressure, Heart Rate) • Hospitalizations &/or clinic visits & paracentesis • NYHA classification • TTE measurements, tricuspid regurgitation & heart function • ECG results • Six minute walk test (pre & post walk data & results) • KCCQ & SF-12 questionnaires • Edema Questionnaire • Concomitant Medications and doses¹ • Adverse events • mRS (if applicable) | 
 • Date of blood draw • WBC • RBC • Hematocrit • Hemoglobin • Platelets • ALT/SGPT • AST/SGOT • Bilirubin • LDH • GGT • ALP • Albumin • Sodium & potassium • Urea • Serum creatinine and eGFR • INR & PTT/aPTT |

1. *No changes in diuretics are allowed for at least 3 months post procedure unless patient presents with severe hypotension.*

8.7.1 VISIT & ASSESSMENT WINDOWS

Post-procedure follow up visits will be performed on all implanted study patients at 1 month, 6 months, and annually for 3 years post implant procedure intervals as illustrated in Table 11 below:

Table 11 – Follow-up Visit Windows

| Scheduled Follow-up Interval | Follow-up Window |
|-----------------------------------|------------------|
| 1 month (30 days) | ± 7 days |
| 6 months (180 days) | ± 30 days |
| Annually (365 days) up to 3 years | ± 45 days |

Table 12: Screening/Baseline Assessment Windows

| Assessment | Window |
|------------------------------------|--|
| TTE* | Within 60 days of submission to Sponsor |
| TEE** | Within 90 days of submission to Sponsor |
| Hemodynamic Monitoring | Within 90 days of scheduled implant procedure ⁷ |
| Venogram (pacemaker lead patients) | Within 90 days of scheduled implant procedure if venous patency cannot be determined by CT |
| CT Angiogram** | Within 180 days of submission to Sponsor |
| Coronary Angiogram | Within 180 days of scheduled implant procedure |
| Pacemaker interrogation | Within 180 days of scheduled implant procedure |

* TTE must be conducted after informed consent and must be collected according to echo core lab acquisition protocol.

**pre-existing TEE/CT image of adequate quality capturing required anatomy for assessment can be used.

Note: For all imaging (TTE, TEE, CT angiogram, coronary angiogram), if imaging is deemed incomplete or inadequate for assessment, repeat imaging may be required.

Note: Procedure should be scheduled within 90 days of consent.

During the follow up visits, medical information, findings and results will be entered in the appropriate electronic case report forms.

Study patients who have signed the Informed Consent, have met all eligibility criteria, and have the study procedure attempted (at least skin incision to introduce the FORMA system) are considered enrolled in the study.

Patients who enter the procedure room but who do not have the study procedure attempted (at least skin incision to introduce the FORMA system) will be classified as

⁷ If the screening echo confirms the PAP meets the study criteria, the right heart catheterization/hemodynamic assessment at the baseline evaluation may be waived.

“non-implanted” and will be followed 30 days for safety. These patients will be exempt from all other study follow up visit procedures.

Final

Table 13 – Summary of Required Study Procedures

| STUDY PROCEDURES | BASELINE | IMPLANT PROCEDURE ¹ (Day 0) | DAY 1 (24-48 hrs) | DISCHARGE ² | 1 MONTH (30 ± 7 days) | 6 MONTHS (180 ± 30 days) | ANNUAL (for 3 yrs) (365 ± 45 days) |
|---|----------------|---|----------------------|------------------------|---------------------------|-----------------------------|--|
| Informed Consent | X | | | | | | |
| Patient Demographics & Medical History | X | | | | | | |
| Clinical Evaluation/Concomitant Medications ³ | X | | X | X | X | X | X |
| Edema grading, ankle circumference measurements & Patient Edema Questionnaire | X | | | X | X | X | X |
| Hospitalizations &/or clinic visits & paracentesis | X | | | | X | X | X |
| NYHA Class Assessment | X | | | | X | X | X |
| Health Status Questionnaires KCCQ, SF-12 | X | | | | X | X | X |
| Six Minute Walk Test | X | | | | X | X | X |
| Katz Index (ADL), Clinical Frailty Score© | X | | | | | | |
| Patient Preference Survey | X | | | | | | |
| Safety Evaluation | | X | X | X | X | X | X |
| Pacemaker interrogation (pacemaker patients) | X | | | | | | |
| Coronary angiogram (within 1 year of procedure) | X | | | | | | |
| Complete Metabolic Panel and Liver Panel | X | | X | X | X | X | X |
| CBC and Platelet Count | X | | X | X | X | X | X |
| INR & PTT/aPTT | X | | X | X | X | X | X |
| βHCG | X ⁴ | | | | | | |
| Serum creatinine and eGFR | X | | X | X | X | X | X |
| Troponins and CK-MB | X | | X | X ⁵ | | | |
| ECG | X | | X | X | X | X | X |
| Transesophageal Echocardiogram | X | X | | | | | |

¹ Implant procedure should be scheduled within 90 days of consent. Patients who enter the procedure room but who do not have the study procedure attempted (at least skin incision to introduce the FORMA System) will be classified as “non-implanted” and will be followed 30 days for safety. These patients will be exempt from all other study follow up visit procedures.

² Discharge from hospital/unit post implant procedure.

³ No changes in diuretics are allowed for at least 3 months post procedure unless patient presents with severe hypotension.

⁴ βHCG for women who are not sterile or post-menopausal.

⁵ Only required if an elevation was noted post implant (within 48 hours).

⁶ mRS will be conducted at baseline for all patients with a history of stroke. For patients who experience a stroke during the study, mRS will be conducted closest to 90 days post event. It is recognized that an assessment of stroke is incomplete without an appropriate measurement of the disability resulting from the stroke, hence, mRS closest to 90 days post event will be used to assess clinical disability. Every effort should be made to have a neurologist or neurology fellow perform the neurological assessments, or alternatively, a trained research team member certified in stroke assessment. mRS can be obtained by a certified research team member via phone interview with the patient or caregiver member if the patient is unable to visit the research office.

| | | | | | | | |
|--|----------------|---|--|----------------|----------------|----------------|----------------|
| Transthoracic Echocardiogram | X | | | X | X | X | X |
| Pre-Implant Procedure Imaging (CT/ Angiographic Imaging & venogram for cardiac lead patients, if required) | X | | | | | | |
| Ventriculogram Imaging | | X | | | | | |
| Invasive Hemodynamic Monitoring | X | X | | | | | |
| Modified Rankin Scale | X ⁶ | | | X ⁶ | X ⁶ | X ⁶ | X ⁶ |

Final

8.8 MISSED PATIENT VISITS

The Investigator shall inform study patients of the importance of returning for scheduled follow-up visits and reporting any address or telephone number changes. The Investigator shall make every attempt to follow the study patients.

The Investigator shall keep a separate log of the patients' names and current contact information to facilitate their record keeping and ability to contact the patients for future follow-up. If a patient cannot be reached for a follow-up assessment, the Investigator will document the missed visit and effort made to contact that patient, the patient's primary health care provider, and/or hospital records on the appropriate Case Report Form. Patients who miss a visit will not be considered withdrawn, and an effort to contact them at the next follow-up visit interval will be made by the Investigator.

8.9 WITHDRAWAL CRITERIA AND PROCEDURES

The Investigator will make every attempt to follow the patients at each of the required assessment periods. The reason for the withdrawal will be documented on the appropriate case report forms and in the medical records for each patient who has withdrawn.

Patients may be withdrawn from the study for any of the following reasons:

- Patient Withdrawal
The patient may voluntarily withdraw from the clinical study at any time, without penalty or loss of benefits to which they are otherwise entitled.
- Physician Withdrawal
The Principal Investigator also has the right to withdraw a patient if s/he feels it is in the best interest of the patient to do so.
- Lost to Follow-up
If a patient cannot be reached for a follow-up visit, the Investigator will document the contact efforts made to the patient and/or effort to obtain hospital records in the appropriate electronic case report form. If the patient cannot be reached in any way, or misses a visit, the patient will be considered "unable to contact" for that time interval. After three (3) documented attempts to make contact prove unsuccessful, a certified letter will be sent to the patient's residence. If there is no response after the certified letter is sent, the patient will be considered "lost to follow-up."

In all cases of withdrawal (as described above), withdrawn patients will not undergo further study follow-up procedures after the time of study exit. A study patient that has been withdrawn from the study will not be replaced.

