6 STUDY DESIGN

This is a multi-site, prospective, early feasibility study designed to evaluate the safety and function of the FORMA System.

A total of sixty patients will be enrolled in the study. All enrolled study patients will be assessed for clinical follow-up at the following intervals: 1 month, 6 months, 1 year and annually for 3 years post implant procedure.

A description of each study visit and required study procedures is included in Section 8.0, Procedures and Methods. In addition, a summary of required procedures is listed in Table 13.

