- Causal relationship to device and implant procedure

The AE eCRF should be completed as soon as possible thereafter.

The Investigator (or designee) shall provide source documents related to reported adverse event as requested by Sponsor or their designee.

The Sponsor will evaluate all adverse events for reportability as an UADE in accordance with 21 CFR part 812.46(b). The Investigator and Sponsor will comply with reporting requirements per 21 CFR part 812.150. A Sponsor who conducts an evaluation of an UADE under 812.46(b) shall report the results of such evaluation to FDA and to all reviewing IRB's and participating Investigators within 10 business days after the Sponsor first receives notice of the event. Thereafter the Sponsor shall submit such additional reports concerning the event as FDA requests.

In addition, the Investigator will report all adverse events to their Institutional Review Board and / or National Regulatory Agency in accordance with the applicable requirements.

Finally, the Investigator should follow all unresolved adverse events until the events are resolved or otherwise explained, or the patient is lost to follow-up or has withdrawn consent.

12.3 FINDINGS EXPECTED TO OCCUR WITH TREATMENT OF TRICUSPID REGURGITATION AND/OR INTERVENTIONAL CARDIAC PROCEDURES THAT DO NOT REQUIRE REPORTING TO THE SPONSOR

For purposes of this study, the following findings are not considered adverse events requiring reporting to the Sponsor. These findings are normally expected to occur in association with treatment of tricuspid regurgitation, and/or are associated with customary, standard care of patients undergoing interventional cardiovascular interventions:

- Post-procedure pain (within 48 hour of procedure) not requiring treatment or treated with non-opioids
- Emesis, nausea, or headache (within 48 hours of procedure) associated with anesthesia
- Out of range (outside the standard laboratory normal value) or "abnormal" lab values (including electrolyte imbalance) that are not clinically significant and do not require correction.

Note: Abnormal lab values that roll up to a diagnosis should not be reported as separate AEs (e.g. increased K+ in patient with renal insufficiency; elevated white blood count without signs or symptoms of infection)

- Low grade temperature increase without signs and symptoms of infection

- Minor, localized tenderness, swelling, induration, oozing, etc. at access site(s)

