| Thrombus (Device Thrombosis) | 
An aggregation of platelet, fibrin, clotting factors, and other cellular elements exclusive of infection.
 
Device thrombosis is defined as any thrombus in the absence of infection attached to or near the investigational device that interferes with function of the device. An investigational device related thrombus may be confirmed by operation, autopsy, or diagnostically by such methods as echocardiography, angiocardiography, or magnetic resonance imaging.
 |
| Transient Ischemic Attack (TIA) (MVARC) | See “Stroke/TIA” |
| Tricuspid Regurgitation | Tricuspid Regurgitation (TR), tricuspid insufficiency or tricuspid incompetence describes a condition in which blood flow through the tricuspid valve flows in the incorrect direction during part of the cardiac cycle. |
| Unanticipated Adverse Device Effect (UADE) (FDA) | Any serious adverse effect on health or safety or any life-threatening problem or death caused by, or associated with, a device, if that effect, problem, or death was not previously identified in nature, severity, or degree of incidence in the investigational plan or application (including a supplementary plan or application), or any other unanticipated serious problems associated with a device that relates to the rights, safety, or welfare of patients. |
| Valvular Leak (See Also “Nonstructural Dysfunction”) | Any evidence of leakage of blood through the native valve leaflets and around the investigational device. Diagnosis of valvular leak may be obtained from echo; however definitive diagnosis is obtained at reoperation, explant, or autopsy. |

| | |
|-----------------------------------|--|
| Withdrawal by Investigator | A patient who consents to participate in the study and is enrolled but is withdrawn by the Investigator. |
|-----------------------------------|--|

Final

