## 6. DATA AND ANALYSIS CONVENTIONS

### 6.1 General Conventions

- For continuous variables, summary statistics will include number of observations, mean, median, standard deviation, minimum, maximum, and 95% confidence intervals (based on normal distribution) per table shells. Nonparametric techniques may be used if the data does not meet the assumptions of parametric tests.
- For ordinal data, the count and percentage of patients will be presented.
- For categorical and qualitative variables, summary statistics will include number of observations, percentage, and 95% Clopper-Pearson confidence intervals per table shells. In general, the denominator for the percentage calculation will be based on total number of patients with evaluable data for a specified time point unless otherwise specified. Patients with missing data will be excluded from the denominator.
- Survival analysis techniques will be used to analyze the time-to-event variables. Summaries will include the number of patients at risk, number of events, number of patients with the event, and Kaplan-Meier estimates at given time points. Patients without events will be censored at their last known event-free time point. If this event-free time point occurs after the analysis time point, the days to event variable will be set equal to the analysis time point so that the patient will be included in the analysis. For patients who did not have an event or early withdrawal and have not yet completed the analysis visit, they will be censored at their last participation date. Standard errors will be calculated using Greenwood's formula and SAS defaults will be used for confidence bands and transformations on  $S(t)$  for the confidence limits. Kaplan-Meier event rate plots will be presented via the cumulative hazard rate plotted against the days from implantation.

- [REDACTED]

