### 6.2 Handling of Missing Data

All statistical analysis on the endpoints will be performed using only those patients with available data required for endpoint analysis. No missing value imputation will be performed.

 Edwards	Revision Date: April 1, 2019		Rev	3.0	For Use Only by Affiliates of Edwards Lifesciences	Page 15 of 18
	Title	Statistical Analysis Plan for FORMA EFS				

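### Physician withdrawal after implant ends study follow-up with no provision for vital status or new events, so withdrawals linked to prognosis could bias the later results

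*Protocol*

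**What the plan says.** Protocol 8.9 lists physician withdrawal beside patient withdrawal and loss to follow-up: "The Principal Investigator also has the right to withdraw a patient if s/he feels it is in the best interest of the patient". For every type of withdrawal, "withdrawn patients will not undergo further study follow-up procedures after the time of study exit". The reason is recorded, and "A study patient that has been withdrawn from the study will not be replaced". Protocol 8.10 then exits the patient from the study.

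The clause reaches treated patients. Protocol 18 defines withdrawal by the investigator as "A patient who consents to participate in the study and is enrolled but is withdrawn by the Investigator", and Protocol 8.2 sets enrollment at skin incision.

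Protocol 12.2 has a different stopping point for one kind of data. Sites are asked to "follow all unresolved adverse events until the events are resolved or otherwise explained, or the patient is lost to follow-up or has withdrawn consent". A physician's decision to withdraw is not on that list.

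On analysis, SAP 5.1 makes the last participation day the Kaplan-Meier censoring day. SAP 6.1 says "Patients without events will be censored at their last known event-free time point" and takes patients with missing data out of percentage denominators. SAP 6.2 has endpoint analyses "performed using only those patients with available data required for endpoint analysis", with no imputation. SAP 7.1 tabulates disposition at each interval. No sensitivity analysis for withdrawal is described.

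**The concern.** The treatment is a one-time permanent implant. A patient withdrawn by the investigator after Day 0 may still carry the device, and from that date the study has no planned way to learn of a death, a new hospitalization, a reintervention or a device event. The trigger is a judgement about the individual patient, so it may well be related to prognosis. Censoring at last participation and dropping the patient from denominators both treat the withdrawn patient as resembling those who remain. If the withdrawn do worse, later event rates come out too low and later success rates too high.

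The stated purposes include safety and function, clinical outcomes to 3 years (Protocol 2), and guidance for later studies (Protocol 4). With 60 patients, two or three unobserved outcomes are noticeable.

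**Working it through.** **There is no figure of the plan to reproduce.** Protocol 13.1 and SAP 2.3 set 60 patients without statistical justification. No event rate, withdrawal rate, alpha, power or dropout allowance is given.

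**Step 1: what is collected after each kind of exit**

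| Situation | Collection afterwards | Source |
|---|---|---|
| Missed visit | Not a withdrawal; contact again at next interval, provider and hospital records tried | Protocol 8.8 |
| Explant | 30 days of safety evaluation, up to 180 days for unresolved explant-related events | Protocol 8.10 |
| Study terminated | Follow-up continues per protocol | Protocol 16.6 |
| Physician withdrawal | Unresolved adverse events only; no stated collection of vital status or new events | Protocol 8.9, 12.2 |

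**Step 2: which results are exposed**

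- Not exposed: device success, fixed at exit from the catheterization laboratory (SAP 8.2).
- Exposed only if withdrawal comes before the assessment: procedural success (discharge), and MAE and clinical success (30 days).
- Most exposed: time to first heart failure re-hospitalization and re-hospitalization rates (SAP 8.4.2), late adverse events (SAP 8.4.3), FDA device success at later visits (SAP 3.3.1), and FDA individual patient success at 6 months and 1 year (SAP 3.3.3).

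**Step 3: illustrative size (assumptions, not document figures).** Take N = 60, the upper limit for the as-treated cohort, with E true events by 1 year. Suppose w of those E patients are withdrawn just before their event.

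Percentage under SAP 6.1: (E − w)/(60 − w).

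Kaplan-Meier under SAP 6.1: 1 − ∏(1 − 1/n_i), where n_i is the number at risk at each observed event. Events are spread evenly over days 20 to 350, the w withdrawals are spread evenly among them, and everyone else is followed to day 365. For E = 12 and w = 3 this is 1 − (54/59)(49/53) = 15.4%.

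| True rate | w | Percentage | Kaplan-Meier, 1 year |
|---|---|---|---|
| 12/60 = 20.0% | 1 | 11/59 = 18.6% | 18.6% |
| | 3 | 9/57 = 15.8% | 15.4% |
| | 6 | 6/54 = 11.1% | 10.5% |
| 18/60 = 30.0% | 1 | 17/59 = 28.8% | 28.8% |
| | 3 | 15/57 = 26.3% | 25.7% |
| | 6 | 12/54 = 22.2% | 21.1% |

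Loss per withdrawal: smallest (30.0 − 28.8)/1 = 1.2 points, largest (20.0 − 10.5)/6 = 1.6 points.

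The 95% Clopper-Pearson interval is 10.8% to 32.3% for 12/60 and 18.8% to 43.2% for 18/60. With w = 3 every estimate lies inside. With w = 6 and a true rate of 20%, the estimates are at or just past the lower limit.

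**Step 4: direction.** If the withdrawn patients would have been event-free, the shift reverses: with three of them, 12/57 = 21.1% against 20.0%. The direction depends on who is withdrawn.

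**The case against.** The strongest reply is that nothing directs investigators to withdraw patients who deteriorate. Protocol 8.9 opens by asking for every attempt at follow-up, and 8.8 keeps patients who miss visits in the study. Reasons are documented and disposition is tabulated, so physician withdrawals would be visible. The study is descriptive, so no test or power is affected, and the main endpoints fall at or before 30 days. All this stands and limits the weight of the point. It does not supply outcomes after withdrawal.

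Several stronger readings are tempting and are not supported:

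- A reader might infer that all follow-up stops. Protocol 12.2 still has unresolved adverse events followed. The gap is new events, vital status and effectiveness data.
- A reader might see a contradiction with Protocol 6, where "All enrolled study patients will be assessed for clinical follow-up at the following intervals". That is the general visit schedule; 8.9 and 8.10 state exceptions to it. The mismatch needing reconciliation is between 8.9 and 12.2.
- A reader might say that withdrawal ends nothing but observation. The footnotes to Protocol Tables 9, 10 and 13 restrict diuretic changes for at least 3 months with one exception, so withdrawal may also release a patient from a protocol constraint. That could itself be a prognosis-related reason for withdrawal.
- A reader might project large 3-year distortions by supposing that a fifth of would-be events are lost. With assumed 3-year risks of 58% or 73%, that requires 0.2 × 0.58 × 60 = 7 or 0.2 × 0.73 × 60 = 9 such withdrawals, for which the documents give no basis. A patient withdrawn after a first heart failure re-hospitalization already counts as an event in that curve.

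**Conclusion.** The gap is real and the rules permit bias; the documents do not show that bias occurs or how many physician withdrawals to expect. It concerns the later results only, and the direction is often, not necessarily, in the device's favour. Under the assumptions above (60 patients, a true event rate of 20% or 30%, each withdrawn patient a would-be event), each withdrawal costs about 1 to 2 percentage points, and a few stay within the sampling uncertainty of a study this size. Because every modelled withdrawal is a would-be event, these figures are unfavourable cases and not expected values. The point merits correction as an inexpensive improvement: outcomes lost after withdrawal may not be recoverable later, and the patients concerned may still carry the device.

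**What to change.** **Protocol 8.9 and 8.10.** State that physician withdrawal of a patient in whom the procedure was attempted ends on-site study assessments only. Vital status, hospitalizations, reinterventions and device or adverse events continue to be collected by telephone or from records at the scheduled intervals, unless the patient withdraws consent and as far as the signed consent allows. Reconcile 8.9 with 12.2 on unresolved adverse events. This concerns data collection only, not clinical management.

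**SAP 6.1 and 6.2.** Keep these patients in the Kaplan-Meier risk set and the event denominators through their last remote contact. Add a sensitivity analysis that counts physician withdrawals without later data as events, or as failures for success endpoints.

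**Cost.** A written amendment agreed with the regulatory agency and IRB (Protocol 16.5), SAP text, and a few extra contacts by existing site staff. Record checks and telephone contact already feature in Protocol 8.8 and 8.7. The first 30 patients, enrolled before Rev L (SAP 4), follow the version they consented to, so the change may not reach all of them. Remote contacts give no echo or walk-test data, and late rates may look slightly less favourable.
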